3.3 Outcome variables

Primary Outcomes

Sleep efficiency: As aforementioned, increased dietary potassium may plausibly modify sleep quality, as previously seen in an interventional study by Drennan et al (46), through mediation of improvements to autonomic function (19) and improved vascular function by restoring baroreflex function (15) and improving endothelium-dependent vasodilation (47).

This is measured by using 7-d wrist actigraphy (MotionWatch8, CamNTech Ltd, Cambridge, UK) according to previously published procedures (7). Sleep quality (%) is measured as the amount of time spent asleep/ total amount of time spent in bed.

12-day mean nocturnal glucose: Potatoes may improve nocturnal glucose through several pathways, involving increased dietary quality (48), such as increased vitamin C (49), increased dietary potassium (50) and increased satiety, when compared to alternative starches (51).

Nocturnal measures were chosen to assess glycaemic regulation without the confounding influence of food intake. Whole sleep-time glycaemia parameters will be analysed is, and further sub analysis will

be done pre- and post-sleep, and mid-point to investigate potential differences according to sleep stages.

CGM (Abbott Freestyle Libre 3) will be used to measure glycaemic control for 12 consecutive days. The principal investigators have recently reported on the high precision of the Abbott CGM (52). Twelve days has been selected as the 1st and last day of the CGM period may give unreliable results, therefore day 1 and 14 will be excluded from the analysis.

Secondary outcomes

Other nocturnal glucose markers: We will further analyse 12-day nocturnal area under the curve, glycaemic variability (GV), time in range non-diabetic population (TIR_{ND}). GV reflecting glucose fluctuations, are more strongly associated with oxidative stress than prolonged elevated glucose and glucose nadir and peaks, including the number and size (% change from pre-meal baseline) due to the association of glucose nadirs with hunger, satiety, alertness and energy intake (at subsequent meals and over 24 h period) (53) and peaks with oxidative stress and impairment in glycaemic control. Increased TIR_{ND} is associated with improved cardiometabolic markers (lower HbA1c, HOMA-IR, and 10-y ASCVD risk) and with poorer glucose tolerance when TIR is low (higher 1- and 2-h OGTT glucose) (54).

Daytime glycaemic control: Additionally, we plan to look at the same markers across 12-day daytime and 24-hour period.

Endothelial function: Impaired nitric oxide (NO) production causes endothelial dysfunction and increases risk of CVD (55). Capacity to synthesize NO can be assessed by ultrasound imaging of brachial arterial diameter before and after hyperaemia to determine FMD, regarded as the most reliable *in vivo* index (56). Measurements (and blood samples) will be taken at the same approximate time of day to account for circadian fluctuations, and by the same operator to reduce measurement error. All videos will be analysed using a custom MATLAB program (VidArt V13.5, [name], Department of Biomedical Engineering, Maastricht University Medical Center (MUMC)+, Maastricht, The Netherlands)

Heart rate variability (HRV) and blood pressure (BP): Improved HRV, a parameter of cardiac autonomic function, and BP are plausible health benefits of white potato consumption due to increased potassium intakes. Previous intervention studies have reported an improvement in clinic BP following potato consumption (18); however, the effects of potato intake on HRV have not been investigated to our knowledge. HRV is an indirect measure of autonomic nervous system function and predictive of risk of sudden cardiac death (57).

HRV will be measured using a small wireless heart rate/ECG monitor that continuously records interbeat intervals (eMotion Faros 180, Mega Electronics Ltd) to calculate 48-h, daytime and night-time parameters using Cardiscope Analytics software (HASIBA Medical GmbH) (58) Building on prior HRV analysis expertise (58, 59, 60), this will provide novel data on a hitherto unexplored risk factor for hypertension, T2D, chronic kidney disease and CVD events in relation to potato consumption, and will provide important mechanistic information underpinning the 3 primary outcomes. BP will be measured at home using optical blood pressure monitoring via a bracelet. 2-hour averages will be obtained continuously for 12-weeks.

Diet quality will be measured using dietary indices associated with health including PDI (61) (uPDI, hPDI), aMED (62), aHEI (62) and HFD (63, 64) to demonstrate the impact of potatoes on overall diet quality and for inclusion as a covariate in analysis.

Body composition: Weight will be measured (weekly) using home weighing scales. Percentage body fat will be assessed (baseline & endline) using bio-electrical impedance, and waist circumference will be measured with a tape measure at clinic visits.

Blood biomarkers: Plasma lipids (total, HDL-, and LDL-cholesterol and TAG, and calculated TC:HDL-C ratio) will serve as clinically relevant biomarkers of metabolic dysregulation alongside fasting plasma glucose, insulin and HbA1c. Urine and serum potassium will be used to assess compliance as well as a potential stratifier in the analysis of outcomes.

Urinary calystegine biomarker: Calystgeines will be analysed as an exploratory biomarker of potato consumption (a polyhydroxylated nortropane alkaloid) (65) by Triple Quadrupole mass spectrometry (MS/MS). This will accompany existing self-reported compliance records and increase the reliability of this outcome. To our knowledge, this will be the first time this biomarker has been used in a clinical trial setting.

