4.0 Sample Size, Statistics, Selection and Withdrawal of Participants

4.1 Sample size

This study aims to recruit a total of 80 men and women, 1:1 intervention to control, to have 68 people (~15% dropout) complete the study. 34 people in each arm will provide 80% power to detect a difference of 0.468 mmol/L nocturnal glucose concentrations (SD 0.61), based on our CGM data from PREDICT 1 (unpublished data). Additionally, only 24 people are needed to provide 80% power to detect a difference of 4.2% sleep efficiency units, with SDs based on our previous sleep extension intervention (SLuMBER study) (7). These parameters are based on a significance level of 0.025, for two outcomes (calculated with *G*Power* software)

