4.2 Study statistical plan

Mean differences between groups will be assessed at endpoint, adjusting for baseline values and other potential other covariates (maximum 3, as per the rule of 1 covariate per 10 participants).

For the outcomes with 3 timepoints (urinary Na, K, Na:K and calystegines), this will be assessed using a using Linear mixed models (mixed command) with change being the dependent factor, participant ID as random effect, treatment and season as fixed effects, and baseline outcome as a covariate. Variables with 2 timepoints (all other outcomes) will be assessed with an ANCOVA regression model (regress command), with baseline as a covariate. BMI, sex and age may also be covariates depending on the balancing of the arms. Sex differences will also be explored in some outcomes with known sexual dimorphisms, with the use of a sex interaction term.

A 2 -sided P value <0.05 will be considered as showing statistical significance.

Normality will be assessed visually with histogram and Q-Q plot of residuals, and heteroscedasticity with a fitted-residual plot, to satisfy the model assumptions.

We will primarily analyse outcomes on an intention-to-treat basis, analysing participants as randomised. Per-protocol analyses—restricted to participants meeting prespecified adherence criteria—will be performed to assess robustness.

All statistics will be run on Stata/MP 18.0.

[figure not shown]

Figure 5. Flow chart of the recruitment procedures

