5.2 Risks/burdens

Venepuncture

Foreseeable discomfort may be experienced with the venepuncture such as:

- Stress regarding the process
- Insertion of the needle
- Minor bleeding on the area where the needle was inserted. This will be covered with a bandage to minimise the bleeding and reduce skin exposure.
- Minor bruising and/or irritation on the skin. This is normal and will typically last 2-3 days.

- A sore arm. This is normal and will typically last 1-2 days.
- During and/or after the blood sample, a participant may feel dizzy and/or faint. Should fainting occur, the participant will receive all the medical care required until they are fit to leave the Metabolic Research Unit.

To minimise these risks, a trained phlebotomist will conduct the venepuncture procedure.

Equipment

For some volunteers, the requirement of self-applying equipment might cause some stress regarding technical capabilities. To reduce this all volunteers will be well trained through supplied multimedia resources, a 1:1 induction with a study team member and will have continued access to the study team in case of any queries.

CGMs may cause slight discomfort in their application, as a very small needle will puncture the skin to sit just below the skin which will measure interstitial fluid glucose levels. As the sensor protrudes a few cm above the skin, there is a small risk that the sensors can get caught on everyday objects and rip out. To reduce this risk, sensor patches will be provided to cover the whole sensor and keep it fixed to the arm. There may be minor bleeding from the insertion of this needle, in which case participants are instructed to apply some pressure. If the bleeding does not stop after a few minutes of applying pressure, the sensor will be removed and reported to the study team. There is also the possibility of skin irritation to adhesives. If this is the case, the CGM should be removed, and the research team should be instructed for further action.

Participant burden

The initial screening and run-in session (as outlined in section 3.4, study flow), will be held remotely, via online documents and video/telephone calls. This we believe will reduce participant burden in needing to attend in-person clinics, thereby increasing study retention, and may further increase the comfort of the individuals.

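### The 12-day nocturnal glucose endpoint has no rule for shortened sensor wear, its fixed-day exclusion does not match its own reason, and a failed baseline sensor removes a participant who has a valid endline

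*Combined protocol and SAP*

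**What the plan says.** The synopsis makes mean nocturnal glucose over 12 days a primary endpoint, measured at baseline and at week 12. Section 3.3 calls for 12 consecutive days of CGM recording and explains that "the 1st and last day of the CGM period may give unreliable results, therefore day 1 and 14 will be excluded from the analysis".

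Section 5.2 describes how wear can end early. There is a small risk that "the sensors can get caught on everyday objects and rip out", for which patches are supplied. If bleeding at insertion does not stop, "the sensor will be removed and reported to the study team". A skin reaction to the adhesive also leads to removal, followed by unspecified further action.

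The wear length differs between sections. The run-in training list (5.4, schedule of visits) gives 12 days for the CGM. The equipment overview (5.6) gives 14 days, which agrees with the day numbering in 3.3.

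For two-timepoint outcomes, which include glucose, section 4.2 says that they "will be assessed with an ANCOVA regression model (regress command), with baseline as a covariate". It states an intention-to-treat analysis of participants as randomised and gives no missing-data method.

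Section 4.1 says that "34 people in each arm will provide 80% power to detect a difference of 0.468 mmol/L nocturnal glucose concentrations", with SD 0.61, and adds: "These parameters are based on a significance level of 0.025, for two outcomes". Eighty are recruited so that 68 complete, allowing about 15% dropout.

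**The concern.** The plan does not say how to score a record that ends before day 14. It gives no minimum number of valid nights, no rule for which day counts as the last when wear is short, and no rule for combining a replacement sensor with the one it replaced. By contrast, section 3.2 does set validity rules for the 24-hour urine collections, through a creatinine index and a minimum volume.

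Two analysts could therefore follow the text and obtain different primary results from the same data. One might discard a participant whose sensor stopped on day 9. The other might average the nights available and keep the day that the plan distrusts.

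Separately, a complete-case regression on baseline discards a participant whose baseline sensor failed even if the endline record is complete. That sits badly with analysing everyone as randomised. In both cases a person who completed the trial can leave the primary analysis for a device reason, and the sample size allows only for people who do not complete.

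**Working it through.** **1. The exclusion rule against its own reason.** The reason in 3.3 is about the first and last day of the CGM period. The rule removes days 1 and 14.

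- Full 14-day wear: days 2 to 13 remain, which is 12 days. Rule and reason agree.
- Sensor ending on day 9: day 1 is dropped and days 2 to 9 remain, which is 8 days. The last day stays in, as 1/8 = 12.5% of the analysed days. Because the endpoint uses sleep windows only, a sensor lost during day 9 may contribute no night after that, so 12.5% is an upper illustration.
- Replacement sensor, if one is fitted: its first day is not day 1 of the period, so it stays in.
- 12-day wear, as in the run-in list: there is no day 14. Days 2 to 12 remain, which is 11 days, and everyone's last day is included.

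**2. The plan's own power figure.** Inputs from 4.1: difference 0.468 mmol/L, SD 0.61, alpha 0.025, 34 per arm. Section 4.1 does not state sidedness; two-sided is taken from 4.2. Standardised difference = 0.468/0.61 = 0.767. Exact noncentral t power, two-sided 0.025:

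| Per arm | Power |
|---|---|
| 34 / 34 | 80.5% |
| 34 / 33 | 79.9% |
| 33 / 33 | 79.2% |

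The stated 34 per arm reproduces as the smallest size that reaches 80%. The dropout allowance is used in full: 80 × 0.85 = 68. So this calculation contains nothing for completers without a glucose score.

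**3. What unscored records could cost.** The documents give no sensor-loss rate. As an illustration, assume that 5% of sensors fail in each of the two wear periods, independently, without replacement, and that short records are not scored. The scorable number is 68 × 0.95² = 61.4, taken as 61. On the unadjusted test, 31 and 30 per arm give 75.5%.

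The planned analysis adjusts for baseline. If 0.61 is an unadjusted SD (not stated), the residual SD is 0.61 × √(1 − r²), where r is the baseline-to-endline correlation, which is also not given. Ignoring the one degree of freedom spent on the covariate:

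| Assumed r | Residual SD | Power at 68 | Power at 61 |
|---|---|---|---|
| 0 | 0.610 | 80.5% | 75.5% |
| 0.3 | 0.582 | 84% | 80% |
| 0.5 | 0.528 | 91% | 87% |

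**4. What scoring shorter records would cost.** With night-to-night intraclass correlation ICC, the variance of a k-night mean is proportional to ICC + (1 − ICC)/k. Five nights against twelve, ICC assumed:

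- ICC 0.7: 0.760/0.725 = 1.05, so 5% more variance.
- ICC 0.5: 0.600/0.542 = 1.11, so 11% more.
- ICC 0.3: 0.440/0.358 = 1.23, so 23% more.

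**The case against.** A reader might infer that the trial is underpowered for glucose because sensors will fail. The documents do not support that. They give no failure rate, call detachment a small risk, supply patches against it, and in 7.1 describe asking about sensitive skin and plaster allergy beforehand. The bleeding described is at insertion, so it is a failed application and not a record cut short part-way. Power falls only if short records go unscored. The 80.5% and 79.2% come from an unadjusted t-test, whereas the plan fits baseline as a covariate, which could more than cover a modest loss. Dropout below 15% would also leave slack. All of this stands.

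A reader might also infer that the plan forces a choice between no score and a contaminated score. It does not. Section 3.3 states a principle before naming days 1 and 14, and those days can be read as that principle applied to a full 14-day wear. Dropping the actual last day of a short wear would be consistent with the same sentence. That is a sensible reading but it is not the written rule, and the plan does not say why the last day is unreliable or whether the reason carries over to a sensor that detaches early.

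The loss of participants with a missing baseline is not special to CGM: it applies to every two-timepoint outcome. That widens the point and does not answer it.

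**Conclusion.** The concern holds as a gap in the definition and analysis of a primary endpoint. The fixed-day exclusion departs from its stated reason whenever wear is not exactly 14 days, the documents disagree on whether it is 14, and the regression as written drops participants who have a valid endline but no baseline. These conclusions rest on the text alone.

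The size of the effect is unknown. The plan's own calculation has no allowance for unscorable completers, since one fewer in a single arm takes it to 79.9%. Under an assumed 5% failure in each wear, power would lie between 75.5% with no help from baseline and 87% at an assumed correlation of 0.5. The range spans 80%, so no specific power shortfall can be claimed. The firmer reason to act is that the rule for who is scored, and on which nights, is left to the analyst.

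**What to change.** 1. **Section 3.3.** Reconcile the 12-day and 14-day wear lengths with 5.4 and 5.6. Define the primary as the mean over all valid sleep windows in the wear period, excluding the first and last day of each sensor's actual wear, replacements included. Fix a minimum number of valid nights before unblinding. Five is one possible value, but it is a judgement that the documents do not settle. Add a sensitivity analysis restricted to participants with all 12 nights.
2. **Section 4.2.** Keep participants with a valid endline and no valid baseline: set the missing baseline to the mean baseline pooled over both arms and add a missing-baseline indicator. State how the indicator counts towards the limit of three covariates. The same rule can serve the other two-timepoint outcomes.
3. **Section 4.1.** State that the 80% power assumes 68 participants with a scorable glucose endpoint.

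The cost is wording and minor programming, with no new data. Means from fewer nights are slightly noisier, by the 5% to 23% in variance shown above for five nights, and the 12-night sensitivity analysis will show whether that matters. The version under review is dated after the estimated primary completion in the synopsis, but none of these changes depends on further recruitment. Items 1 and 2 need only be settled before the analysis is unblinded.

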3.4 Study Design & Flowchart

Overall study flow diagram is described in Figure 4, and a more detailed event and outcome matrix is summarised in Table 1.

3.5 Population description.

Participants will be aged 40-80 years old. As cardiometabolic health declines with age, this age group is typical of an at-risk population for cardiometabolic health disorders. This declination of health also offers more room to observe intervention improvements when compared to a younger population.

The ethnicity will be reflective of the central London location of KCL. Previously, large dietary intervention trials conducted by the principal investigators, such as: MARINA, RISCK, DRFRUITNVEG and CRESSIDA, have recruited 66-85 % white, 9-10 % South Asian, 5-10 % Black African/Caribbean, and 2-4 % other ethnic groups (30, 39, 66).

Participants will have less favourable self-reported sleep quality scores (<85%) (67), as assessed at screening. This sleep efficiency score has been chosen to allow more scope to detect intervention-lead improvements.

Participants will also consume <4 fruits and vegetables/day, as assessed at screening, which is representative of the typical UK/US diet (25).

3.6 Recruitment methods

Volunteers will be recruited from the public using Kings College emails (circular) and using social media adverts (Twitter, Facebook and Instagram). These methods successfully recruited 164 participants in the CRESSIDA trial (30).

Previous trial participants from the Department of Nutritional Science, who have consented to be contacted, will be emailed.

Lastly, other institutions/universities, with publicly available contact addresses, may be emailed and asked to advertise our study via email and/or poster advertisement.

Drop-outs will be monitored in cohort 1 to assess recruitment targets. We have estimated that recruitment should roughly span one year from the study start.

3.7 Sample screening

Participants will be screened remotely with the use of questionnaires, to match them against the inclusion/exclusion criteria. At baseline clinic, participants BMI will be calculated via calibrated equipment to ensure they're within range. They will also have a finger prick test to measure their fasting glucose, to screen participants for hyperglycaemia ($>7\text{mmol}$). If participants have hyperglycaemia, they will be excluded from the study and be referred to their GP for further tests.

Email exchange: Upon showing interest in the advertisement, participants will be sent a Participant Information Sheet (PIS) along with an online screening questionnaire (using Qualtrics software) which matches participants against the inclusion/exclusion criteria).

Introductory call: All eligible participants will receive a telephone/video call with a member of the study team, both to introduce themselves and the study. This call will serve as an opportunity for participants to ask questions, and to have their understanding of the study checked prior to giving consent. This call also allows the study team to build rapport with participants. After this call, a consent form (Qualtrics software), will be emailed out.

Once consent is remotely obtained, participants will be invited to a virtual 1:1 run-in induction.

An overview of the flow from advertisement to identifying an eligible population, is summarised in Figure 5.

3.8 Inclusion and exclusion criteria

- **Inclusion criteria**
 - Healthy adults
 - Aged 40-80 years old
 - Intake of ≤ 4 portions of fruits and vegetables (excluding potatoes) per day
 - Low sleep quality- $<85\%$ sleep efficiency score on the PSQI
 -
- **Exclusion criteria**
 - Shift workers and those with multiple jobs or carers who are required to wake through the night
 - Unwilling to refrain from dietary supplements
 - Unwilling to follow protocol and/or give informed consent
 - Diagnosed with Cardiovascular Disease (CVD), Type 2 Diabetes, Celiac disease, Insomnia, Sleep apnoea
 - Presence of gastrointestinal disorder
 - Users of drugs that are likely to alter gastrointestinal motility or nutrient absorption
 - History of substance abuse or alcoholism
 - Currently pregnant, planning pregnancy, breastfeeding or having had a baby 12-month prior
 - Weight change of $>3\text{kg}$ in preceding 2-months
 - $\text{BMI} <18.5\text{kg/m}^2$ or $> 35\text{kg/m}^2$,
 - Current smokers, or individuals who quit smoking in the last 6-months
 - Frequently consume wholemeal products (1-2 times per day, in the short screening FFQ)
 - Never consumed refined starchy staple, such as white pasta or rice (rarely or never, in the short screening FFQ)
 - High potato consumption (4-6 times per week, in the short screening FFQ)
 - High risk of obstructive sleep apnoea (answer yes to >3 questions, in STOP-Bang questionnaire)

V5.1 31/08/2025

NON-CTIMP randomised trial

Clinical Trials ref: NCT05994313

REC: HR/DP-22/23-35587

- Vegan
- Sleep-related medications, or medications that may interfere with sleep
- Fasting glucose >7mmol/l (finger prick test at baseline clinic)

Table 2. Event and Outcome matrix

Body composition (Tanita scales)	Researcher	Secondary outcome					✓						✓		
HRV (48-hours and acute response to stress)	Researcher	Secondary outcome					✓						✓		
Weight	Participant	Secondary outcome													✓
Blood pressure	(Automated via bracelet)	Secondary outcome												✓	
4-day food diary + appetite visual analogue scale	Participant Baseline and Endline: 24-hr before clinics Midline: taken at home and sample posted	Dietary data for quality indices/covariates PDI (uPDI, hPDI) aMED aHEI HFD					✓			✓			✓		

[figure not shown]

Figure 4. Flow diagram of RCT process.

